10.1 Practice and Subject Disposition

Practice Disposition: The number of practices approached for study participation, those that subsequently enrolled in the study and those that declined will be given in a CONSORT Diagram.

Subject Disposition: The number of participants approached for study participation either by phone or in person, the number that subsequently consented and enrolled versus not enrolled (including reasons: screen failures, refusals) will be summarized in a CONSORT diagram. The number of participants selected for 12-month follow-up, and who subsequently had complete versus incomplete follow-up will also be given.

10.2 Protocol Deviations

In this cluster randomized controlled trial (Aim 3), where practices are the recipients of the intervention and where the interventions are based upon education and access to CAPTURE and PEF results, it is not anticipated that study intervention will be discontinued at the practice level.

The most likely protocol deviation is missing 12-month follow-up data in those selected for follow-up, which will be summarized in a CONSORT diagram as described in section 10.1.

10.3 Demographic and Baseline Variables

Demographic and baseline variables for patient participants include:

- Age in years at consent
- Sex (Male, Female)
- BMI
- Race (American Indian/Alaska Native, Asian, Native Hawaiian or Other Pacific Islander, Black or African American, White, Unknown or Not Reported)

- Ethnicity (Hispanic/Latino, Non-Hispanic/Latino, Unknown or Not Reported)
- Educational status (Less than High School Graduate, High School Graduate/GED, Vocational/Some College, College Degree, Professional/Graduate Degree, or Not Reported)
- Employment status (Working, Not working, or Not Reported)
- Smoking status (Current, Former, Never, or Not Reported)
- Living arrangement (Alone, Not alone, or Not Reported)
- Insurance provider (Private, Public, None, or Not Reported)
- Baseline FVC
- Baseline FEV₁
- Baseline FEV₁/FVC
- Use of rescue respiratory medication (Yes if participant uses at least one short-acting bronchodilator, No, or Not Reported)
- Use of maintenance respiratory medication (Yes if participant uses at least one of the following: LABA, LAMA or inhaled corticosteroid [ICS]; No; or Not Reported) and type/combination of medications (ICS alone, LABA or LABA alone, LABA combined with ICS, LAMA combined with ICS, LABA combined with LAMA, LABA and LAMA combined with ICS)
- Cardiac morbidity (Yes if participant lists angina, coronary artery disease, heart attack, coronary artery bypass surgery, angioplasty/cardiac stents or congestive heart failure, No, or Not Reported)
- Use of supplemental oxygen (Yes, No, or Not Reported)
- COPD Assessment Test (CAT) Score
- Cohort membership as defined in section 6.1 (Spirometrically Defined COPD, Clinically Significant COPD, Mild COPD, PRISM, SNO, No COPD by Spirometry).

Practice-level baseline covariates include:

- Location (Rural, Non-rural)
- Type of practice (Federally Qualified Health Care Center
 - Part of large health system, ACO or similar (not affiliated with a medical school),
 - Part of academic medical center/health system, Independent practice, Other)
- Presence of a residency program (Yes, No)
- Practice size as defined as the total number of primary care MD/DOs and NP/PAs
- Ability to perform in-house spirometry (Yes, No).

The primary study demographic and baseline variables table will have columns for CAPTURE positive, CAPTURE negative, and overall study populations. A separate demographics table will be constructed with columns depicting spirometrically defined COPD populations.

10.4 Intervention Fidelity

Completion of the clinician education is confirmed by either review of an attendance sheet for group education or online registration of the required educational videos. For patient participants who are enrolled in a CAPTURE intervention site, confirmation of giving the completed and scored CAPTURE screening tool to the patient participant's clinician is confirmed by written affirmation of the research associate completing the patient's study visit. For each practice, we will summarize the percentage of participating clinicians who completed educational training. For practices randomized to the CAPTURE intervention arm, we will summarize the percentage of enrolled participants whose CAPTURE information is provided to clinicians. Summary statistics for each of these variables across practices will be provided.

On-site monitoring visits are conducted to review all scoring of the CAPTURE tool. In the subset of participants where on-site monitoring is conducted, we record: 1) whether or not the CAPTURE Tool

is scored correctly on the source document and 2) whether or not the score is transcribed correctly into the clinical database. We will provide percentages for 1 and 2 overall and by practice.

Additionally, all spirometry tests are reviewed and graded for quality by one of the investigators ([name]). Quality results are reviewed with PBRN teams and any needed retraining completed to achieve the goals of 100% CAPTURE scoring accuracy and 90% interpretable spirometry results. We will define a usable spirometry value for each participant as being of quality A-D. Using this information, we will summarize the percentage of participants with usable spirometry, overall and by practice.

11 Efficacy Analyses for the Cluster Randomized Trial (Aim 3)

11.1 Primary Efficacy Analysis

The primary efficacy analysis is restricted to CAPTURE+ participants, denoted in section 9.3 as population 1 (Primary Analysis Population). The primary analysis will be to compare the average cluster sample proportion (average proportion of CAPTURE+ patients per practice meeting composite endpoint) between intervention arms. Practices that do not identify any CAPTURE+ subjects will not contribute to this analysis. A two-sample test comparing average cluster sample proportions will be used that explicitly takes into account correlation between individuals treated within the same practice. A two-sided p-value < 0.05 will be considered statistically significant. This analysis corresponds to a generalized estimating equation (GEE)⁴ regression analysis with (1) individual-level binary composite outcome data, (2) CAPTURE intervention group as a covariate, (3) practice id used to identify correlated outcomes, (4) exchangeable correlation matrix that assumes similar correlation between all composite outcome results for patients within the same practice, and (5) an identity link function so that the coefficient parameter corresponding to CAPTURE intervention group represents a difference in outcome probability. The primary analysis would then correspond to a test for whether the CAPTURE intervention group parameter is non-zero.

Technical Details of the Primary Analysis:

This analysis is restricted to CAPTURE+ participants (Primary Analysis Population)

Let $\pi_{ij} = P(\text{Participant } j \text{ from Practice } i \text{ Meets the Primary Endpoint})$.

Let $CAPTURE_i = I(\text{Practice } i \text{ Received Basic COPD plus CAPTURE education intervention})$

Let PRACTICE take on values $i = 1, \dots, 100$ denoting the enrolled practices

For the primary analysis, the GEE model takes the form

$\pi_{ij} = \beta_0 + \beta_1 CAPTURE_i$, where binary outcomes from the same practice are assumed to follow a compound symmetry correlation structure.

R code for the Primary Analysis:

If the R dataset representing CAPTURE+ patients is called **final** and variables are

MetComp=1 if individual met primary (composite) outcome, 0 otherwise

CAPTURE=1 if individual was from a practice randomized to the Basic COPD plus CAPTURE education intervention, 0 otherwise

Practice is a variable with values $1, \dots, 100$ denoting the enrolled practices

Then using the **geeglm** function from the **geepack** package, the R code to run the primary analysis is

```
geeglm(MetComp ~ CAPTURE,
       family = binomial(link = "identity"),
       data = final,
       id = Practice,
       corstr = "exchangeable")
```

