9.3.2 PRACTICE BEHAVIOR (AIM 3)

The primary analysis of the Aim 3 primary endpoint will be to compare the average cluster sample proportion (average proportion of CAPTURE+ patients per practice meeting composite endpoint) between intervention arms. Practices that do not identify any CAPTURE+ subjects will not contribute to the primary analysis. The primary analysis is a two-sample test comparing average cluster sample proportions that explicitly takes into account correlation between individuals treated within the same practice. A two-sided p-value < 0.05 will be considered statistically significant. This analysis corresponds to a generalized estimating equation (GEE) regression analysis with (1) individual-level binary composite outcome data, (2) CAPTURE intervention group as a covariate, (3) practice id used to identify correlated outcomes, (4) exchangeable correlation matrix that assumes similar correlation between all composite outcome results for patients within the same practice, and (5) an identity link function so that the coefficient parameter corresponding to CAPTURE intervention group represents a difference in outcome probability. The primary analysis would then correspond to a test for whether the CAPTURE intervention group parameter is non-zero. There are no planned interim analyses for the primary endpoint, the rationale being that this is not a pharmaceutical or device trial that would benefit from standard stopping rules for efficacy. A DSMB will be monitoring the study for safety and study integrity.

Secondary analyses on meeting the composite outcome for participants who are CAPTURE+ will employ the GEE analysis framework with individual and practice level predictors in addition to the CAPTURE intervention group. Interactions will be assessed. We will also use the GEE framework to study and describe each of the individual components of the composite outcome as they relate to individual and practice level outcomes. In the subset of smoking patients, we will use GEE regression analysis to study additional binary outcomes, such as incidence of physician counselling/recommendation to stop smoking, physician referral to a formal smoking cessation program, newly prescribed smoking cessation medication, and referral to a smoking quit line.

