7.3 Randomization and Blinding

Randomization: Practices will be randomized into one of the two interventions, COPD education or COPD education + CAPTURE education, in a 1:1 manner, stratified by PBRN. Randomization will occur at the time of site activation and each site will be assigned a unique randomization number. The DCC will prepare the randomization schedule, using computer-generated block randomization with the block size(s) known only by the DCC. A secure web-based application will be built that will be used by the central study coordinators to enter site information (e.g., site ID, stratification factor) and to obtain the randomization number. The information can be printed and sent and/or emailed directly to the study coordinator.

Blinding: This is a single-blind study with the participants blinded to whether their practitioners have received CAPTURE education and patient-level CAPTURE results. Practitioners at sites that are randomized to the control arm (COPD education alone) will be blinded to the CAPTURE questionnaire and PEF results. All practitioners and participants will be blinded to the baseline COPD status of the participants (i.e., blinded to spirometry results), except for safety reasons. In this situation, participants and their clinician will be notified if a participant's post-bronchodilator FEV₁ is less than 30% predicted. For all other

participants, they and their practitioners will be blinded to research spirometry results. The coordinator should make every effort to conceal the spirometry results from the participants in these latter cases. Study coordinators should also make every effort to conceal the administration of a post- bronchodilator spirometry test from the practice staff so as not to unblind the physicians to abnormal spirometry.

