(<https://www.abdn.ac.uk/hsru/research/research-tools/study-design/>). These calculations assume a type I error of 5% and that the control arm meets the composite endpoint in 5% of CAPTURE+ patients, and the CAPTURE arm meets the composite endpoint in higher percentages (columns of Table 5). There will be variability in the actual number of CAPTURE+ patients per practice. It is standard practice to inflate the number of needed clusters by 12% to account for this extra source of variability. Therefore, our power calculations are based on 44 clusters per intervention arm.

9 General Analysis Considerations

| | | | | | |
|---|-------|------|------|-------|-------|
| Overall power to detect a difference in rate of meeting primary endpoint in CAPTURE group (50 practices/cluster) vs usual care (50 practices/cluster), assuming 5% performance rate in usual care; 50 patients total / practice; assuming 10% prevalence gives 5 CAPTURE+/practice. | | | | | |
| Improvement over usual care | +7.5% | +10% | +15% | +25% | +50% |
| ICC=0.05 | 0.72 | 0.89 | 0.99 | >0.99 | >0.99 |
| ICC=0.10 | 0.65 | 0.84 | 0.98 | >0.99 | >0.99 |
| ICC=0.15 | 0.59 | 0.79 | 0.97 | >0.99 | >0.99 |

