9.4 Covariates and Subgroups

The effect of the CAPTURE intervention will be explored in predefined subgroups of interest with results tabulated (estimated difference in average proportion of CAPTURE+ patients per practice meeting composite endpoint between intervention arms by subgroup, corresponding 95% confidence interval and p-value) as well as displayed via forest plots. These analyses will proceed similarly to that described for the primary endpoint in section 11.1. Individual-level covariates used to define subgroups of interest are categorical age (45-59 years, 60-69 years, 70-80 years), gender (Male, Female), race (American Indian/Alaska Native, Asian, Native Hawaiian or Other Pacific Islander, Black or African American, White, Unknown or Not Reported), ethnicity (Hispanic/Latino, Non-Hispanic/Latino, Unknown or Not Reported), educational status (Less than High School Graduate, High School Graduate/GED, Vocational/Some College, College Degree, Professional/Graduate Degree, or Not Reported), insurance status (private, public, none), living arrangements (alone, not alone), employment status (working, not working, unknown), smoking status (Current, Former, Never), asthma history, baseline respiratory medications (short-acting bronchodilator, maintenance respiratory medication, or none), cardiac morbidity, COPD Assessment Test (CAT) score (10 or above versus less than 10), BMI (Below 25.0 [Normal/Underweight], 25.0-29.9 [Overweight], 30.0-39.9 [Obese], 40.0 and Above [Severely Obese]), as well as cohorts defined in section 6.1 (Spirometrically Defined COPD, Clinically Significant COPD, Mild COPD, No COPD by Spirometry, PRISm, and SNO). Practice level covariates include practice type (Part of large health system/ACO/similar, Part of academic medical center/health system, Federally Qualified Health Care Center, Independent practice, Other), location (Rural, Non-rural), being a residency site, having in-house spirometry, and number of MD/DO/NP/PA primary care clinicians (0-4, 5-9, 10 or More). Because of the possible impact of the SARS-CoV-2 pandemic on study outcomes, these analyses will be repeated in subgroups defined by whether the one-year follow-up period had entirely elapsed by March 19, 2020 (date when PBRNs paused study enrollment due to SARS-CoV-2); that is, the analyses will be repeated separately in the cohort with baseline visit completed on or before March 19, 2019, and separately in the cohort with baseline visit completed after March 19, 2019. Chart review and patient follow-up survey need not be completed by March 19, 2020 for a patient to be categorized as having pre-pandemic follow-up for this subgroup analysis.

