Additional baseline predictors for imputing outcome variables will be included in the imputation procedure based on examination of study data that are blinded with respect to intervention group (pooled across intervention groups), assessing the association of each baseline variable with 1) whether the outcome data is missing, and 2) the outcome itself (among those with complete outcome data). To avoid including extraneous predictors, which may cause problems in fitting the logistic regression models and generating accurate imputations, we will use only baseline predictors that are associated with *both* the outcome missingness *and* the outcome itself, for at least one outcome in the group, based on p-values <0.01 from t tests¹ and chi-square tests². These additional baseline predictors will be selected separately for the medical record review variables and for the follow-up survey variables.

Based on the study data on March 21, 2023, from study sites for which all follow-up data have been collected (representing about 84% of the patients selected for follow-up), the additional baseline predictors for each outcome group would be the following:

| Outcome variable(s) | Predictors for medical record review | Predictors for follow-up survey |
|---------------------------------|--|---|
| Pulmonary care outcomes | PBRN Practice type Practice size (# clinicians) Patient enrollment date Education | Race Education Health insurance Smoking status FEV ₁ % predicted |
| Flu vaccination | PBRN Practice type Practice is a residency site Race Ethnicity Education | PBRN Age Race Education Health insurance Ever had flu shot |
| Smoker-specific outcomes | PBRN Practice type Practice is a residency site Practice size (# clinicians) Education | PBRN |

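### The Aim 3 primary GEE omits PBRN, the randomisation stratum; if outcome rates differ between PBRNs, the test is conservative and some power is lost

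*SAP*

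**What the plan says.** Protocol 6.2 and SAP 7.3 randomise practices "in a 1:1 manner, stratified by PBRN".

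The primary model does not use that stratum. SAP 11.1 describes a GEE with "2) CAPTURE intervention group as a covariate, (3) practice id used to identify correlated outcomes", an exchangeable correlation and an identity link. Its formula has an intercept and one arm coefficient, and its R code begins "geeglm(MetComp ~ CAPTURE" with no further predictor. Protocol 9.3.2 also lists only "2) CAPTURE intervention group as a covariate".

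The secondary multivariable GEEs of SAP 11.2 draw on individual-level and practice-level predictors. The lists that would supply them, in SAP 9.4 ("Practice level covariates include practice type" and so on) and SAP 10.3 ("Practice-level baseline covariates include" and so on), do not name PBRN.

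PBRN does appear in SAP 9.5 as an imputation predictor. Extra predictors had to be associated with both missingness and outcome, "for at least one outcome in the group, based on p-values <0.01". PBRN was kept for the chart-review pulmonary care outcomes, which are the components of the primary composite. It was not kept for the survey versions of those outcomes.

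**The concern.** Stratifying by PBRN balances the arms within each network, so differences in outcome rates between networks cancel out of the arm comparison. A sandwich standard error clustered on practice, from a model with the arm alone, cannot see this. It treats between-PBRN spread as ordinary between-practice noise. If that spread is real, the reported standard error is too large, the test spends less than its nominal 5%, and power is lost.

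At stake are a few points of power on the primary test, mostly at the smallest effect considered. At +7.5% the SAP's stated power is 0.59–0.72 in Table 5 and 0.55–0.76 in Table 10.

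**Working it through.** **Inputs from the documents.** Two-sided alpha is 0.05. SAP 8.2 assumes that "the control arm meets the composite endpoint in 5% of CAPTURE+ patients", with 44 practices per arm after the 12% allowance, 5 CAPTURE+ patients per practice and ICC 0.05, 0.10 or 0.15. SAP 13.1 (Table 10) uses 67 practices and 10 CAPTURE+ each. SAP Table 6 gives practice counts for six PBRNs; SAP 4.1 and 6.1 say seven.

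**Assumed.** The share *f* of the ICC that lies between PBRNs is not in the documents. I took *f* = 0, 0.25 and 0.50.

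**Step 1: reproduce the stated power.** The effective number per arm is 44 × 5 / (1 + 4 × ICC), which is 183.3, 157.1 and 137.5. A two-proportion test then gives:

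| ICC | +7.5% (stated) | +10% (stated) | +15% (stated) |
|---|---|---|---|
| 0.05 | 0.721 (0.72) | 0.894 (0.89) | 0.993 (0.99) |
| 0.10 | 0.654 (0.65) | 0.843 (0.84) | 0.983 (0.98) |
| 0.15 | 0.596 (0.59) | 0.793 (0.79) | 0.968 (0.97) |

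Table 5 reproduces, and its formula has no stratum term. Table 10 reproduces in the same way with 33.5/1.12 = 29.9 practices per arm: at ICC 0.10, 0.655 and 0.844 against the stated 0.65 and 0.84.

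**Step 2: standard error ratio, closed form.** With *n* patients per practice, unadjusted over adjusted SE is

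sqrt{ [ICC + (1−ICC)/n] / [(1−f)·ICC + (1−ICC)/n] }.

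For n = 5, ICC 0.10, f = 0.50: sqrt(0.28 / 0.23) = 1.10. For f = 0.25: sqrt(0.28 / 0.255) = 1.05. For n = 10: 1.07 (f = 0.25) and 1.17 (f = 0.50). At f = 0 the ratio is 1.

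**Step 3: simulation.** Six PBRNs were scaled from Table 6: goals scaled to 18, 17, 17, 7, 17, 12 = 88 practices of 5 patients; and 15, 15, 9, 6, 11, 11 = 67 practices with Poisson mean 10. Arms were permuted 1:1 within PBRN. PBRN means and practice rates were beta-distributed with total ICC fixed and share *f* between PBRNs. There were 8,000 null runs and 5,000 power runs per cell. The unadjusted test is the plain robust Wald test of the SAP code. The adjusted test adds a PBRN factor and multiplies the robust variance by K/(K−q), with K practices and q coefficients. Ranges are over ICC 0.05–0.15; the power row covers +7.5% and +10%.

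| | f = 0 | f = 0.25 | f = 0.50 |
|---|---|---|---|
| 88 practices × 5: SE excess | 0% | 2–5% | 4–11% |
| Unadjusted null rejection | 5.0–5.5% | 4.5–4.9% | 3.8–4.6% |
| Power change from adjusting (points) | −1.1 to −0.5 | +0.1 to +1.0 | +0.5 to +3.9 |
| 67 practices × 10: SE excess | – | 4–7% | 8–16% |
| Unadjusted null rejection | – | 3.9–4.8% | 2.8–4.2% |
| Power change from adjusting (points) | – | −0.1 to +1.8 | +0.9 to +5.1 |

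Examples with 88 practices and ICC 0.10, unadjusted to adjusted, for f = 0, 0.25, 0.50:

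- +7.5%: 0.685 to 0.678, 0.704 to 0.714, 0.731 to 0.757.
- +10%: 0.868 to 0.862, 0.874 to 0.879, 0.895 to 0.911.
- +15%: change under 0.5 point.

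Both estimators had mean bias within 0.001. Simulated SE ratios sit slightly below the closed form because only six PBRNs are drawn.

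**Step 4: a larger bound.** Putting the closed-form ratio straight into a normal power formula, with no degrees of freedom charged for PBRN, gives bigger losses on the Table 5 inputs. At ICC 0.10 and f = 0.50 the loss is 3.7 points at +10% and 6.9 at +7.5%. At ICC 0.15 and f = 0.50 it is 6.1 and 10.1. I rely on the simulation, which draws a finite set of PBRNs and pays for the extra terms.

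**The case against.** The strongest reply is that nothing is broken. The arm-only test is valid, its tabled power is right, and the gain rests on an assumed *f*. At a 5% control rate the SD of PBRN rates is sqrt(f × ICC × 0.05 × 0.95). So f = 0.50 needs an SD of about 3.4–6.0 points around a mean of 5%, which is a wide spread; f = 0.25 needs 2.4–4.2 points and yields at most one point of power on the Table 5 inputs. This stands, and it is why the point concerns efficiency only.

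The evidence that PBRN is prognostic is indirect. The SAP 9.5 screen pooled the arms, used about 84% of patients selected for follow-up, and relied on t and chi-square tests not described as allowing for clustering. Practice-level correlation alone could produce a small p-value. Retention for chart review but not for survey data could reflect recording habits. Nothing is shown for the composite in CAPTURE+ patients. This also stands.

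The primary analysis is complete-case, and survey completion was 65% in March 2020 (SAP Table 9). Smaller clusters shrink the ratio: with n = 5 × 0.65 = 3.25, ICC 0.10 and f = 0.50 it is sqrt(0.377 / 0.327) = 1.07, not 1.10.

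The arm-only model is saturated and cannot give fitted probabilities outside 0–1, whereas the adjusted identity-link model can. That is a real cost, dealt with in the fix.

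Finally, the covariate lists in SAP 9.4 and 10.3 are not closed, so PBRN is not forbidden in the secondary models. It is also not specified in any of them.

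**Conclusion.** The concern holds. Randomisation is stratified by PBRN and the primary analysis ignores it, in the text, the formula and the code. If PBRNs differ, the test is conservative and gives up roughly 0–4 points of power on the Table 5 inputs and up to about 5 on the Table 10 inputs, for +7.5% or +10%. If they do not differ, nothing is lost by leaving PBRN out.

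These sizes rest on the assumed *f*, the planned 5% control rate, six PBRNs and full cluster sizes. At that control rate the effect at +15% or more is negligible. With a higher control rate and wide PBRN differences it would not be: at an assumed 20% control rate, a PBRN SD of 11 points and a residual practice ICC of 0.05, simulated power for +15% was 0.859 without PBRN and 0.912 with it.

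The change is worth making because it is cheap and aligns the analysis with the design, but the trial's validity does not depend on it.

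**What to change.** In SAP 11.1 and Protocol 9.3.2, make the primary model MetComp ~ CAPTURE + factor(PBRN), clustered by practice, with a degrees-of-freedom correction to the sandwich variance. Keep the arm-only model as a sensitivity analysis. Settle this before unblinding, so that the choice between models is not driven by the data.

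Two safeguards belong in the same edit:

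- **Variance correction.** Without it, the adjusted test rejected 5.9–6.5% under the null with 88 practices; with it, 4.6–5.4%.
- **Fallback.** Pre-specify a Gaussian-identity fit with the same robust variance if the binomial-identity fit does not converge or gives a fitted probability outside 0–1. The arm coefficient then remains a risk difference. At a 5% control rate and +10%, the adjusted least-squares identity fit had a fitted probability at or below 0 in 45–81% of simulated trials, so the fallback would be used often. Naming the Gaussian-identity fit outright as the primary model would be simpler.

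The cost is one factor, using five or six degrees of freedom among about 100 practices, plus a few sentences. The price is 0.5–1.1 points of power if PBRN turns out to have no effect.
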